Once eligible patients are identified from institutional registries, the next office appointment for any diabetes-related indication (e.g., chronic disease management provider visit, diabetes educator visit, dietitian visit, diabetes group class, etc.) will be recorded for each patient. These patients will be contacted by telephone by a language-congruent study staff member to introduce them to the study and to assess preliminary interest in participation. Patients will be sequentially recruited at their next office visit until the target accrual is reached. Patients may also be recruited, consented and participate in study activities over the phone.

A language-congruent study staff member will confirm eligibility criteria with the patient and obtain written informed consent in an exam or private room before or immediately after their office appointment. Study staff will then obtain a baseline survey and biometric assessment (see measures) followed by randomization procedures (stratified by gender) and delivery of the digital storytelling intervention (for the intervention group). Each site has developed slightly different protocols for effective recruitment and intervention implementation based on lessons learned from the pilot study. Based on data from our pilot, we expect recruitment and enrollment to occur over a period of no more than 24 months across all sites with the following distribution:

- Hennepin Healthcare: N=240 participants enrolled.
 - Medicine Clinic
 - East Lake Clinic
 - Richfield Clinic
- Mountain Park Health Center: N=215 participants enrolled.

Participant retention will be facilitated in five ways. First, potential participants will confirm the eligibility criteria stating that they expect to receive medical care at the recruitment clinic for at least the next six months (above). Second, appointment cards for both subsequent study visits will be provided to participants after they have completed enrollment. Third, language-congruent study staff will contact patients by phone to remind them about upcoming study visits. Fourth, participants who do not return phone calls from study staff will be sent a letter asking them to call the study coordination to reschedule the appointment. Fifth, participants will receive remuneration at enrollment and at the of the 3 month visit.

Interventions

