The control group will participate in the same usual clinical care for diabetes (e.g., visits with primary care physician, nurse, diabetes educator, dietitian, etc.) as the intervention group. We will control for study coordinator attention time throughout the enrollment and measurement activities. The control group will be offered the digital storytelling intervention package after the study is completed.

Measures

Participant data will be collected at baseline, six weeks, three months, and six months in their preferred language. Biometric measurements will be obtained during clinic visits at baseline and 3 months. The 3 month visit can occur up to 2 weeks prior to the visit due date and up to 4 weeks after the visit due date, to accommodate scheduling limitations during the COVID-19 outbreak. Participants will complete a survey (administered by same language-congruent study staff) to obtain secondary outcomes and theory-based measures (Table 2) at clinic visits or by phone within 2 weeks following the clinic appointment, and during phone calls at 6 weeks and 6 months. Surveys will be verbally administered to participants by bilingual research staff, and responses will be entered directly into an electronic database. Surveys are not printed and given directly to the participants to complete on their own. Participants will also receive appointment reminders (three total) prior to visits or calls.

Additional clinical data will be collected from the electronic medical records. Investigators and data analysts will remain blinded to group assignment throughout the study.

Demographic, health status, acculturation, health literacy, and diabetes knowledge measures. At baseline, study participants will report on the following demographic data: sex, age, ethnicity, country of birth, annual household income, education level, employment status and housing security. Individuals will report on the following proxies for acculturation: time lived in the U.S., primary language spoken at home, and level of English language proficiency on a 5-point Likert scale¹⁰⁷. Health literacy will be measured with the Short Assessment of Health Literacy—Spanish and English¹⁰⁸. Diabetes knowledge will be measured using the Diabetes Knowledge Questionnaire, available in Spanish and English¹⁰⁹.

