The following data will be obtained at baseline from manual abstraction of the electronic medical records: date of diabetes diagnosis, diabetes medications, diabetes microvascular complications (nephropathy, retinopathy, neuropathy), and presence or absence of provider-assigned diagnoses of coronary artery disease, cerebrovascular disease, peripheral arterial disease, and hypertension.

Primary outcome measure. The primary outcome measure will be glycemic control as measured by hemoglobin A1c. The rationale for use of hemoglobin A1c as an indicator of diabetes control is based on national and regional data that demonstrate significant disparities in reaching hemoglobin A1c targets for Hispanic populations compared with non-Hispanic whites^{27,110}. The importance of glycemic control as part of the comprehensive management of diabetes is well documented, and hemoglobin A1c testing is a well-established strategy to monitor glycemic control in patients with diabetes¹¹¹. Hemoglobin A1c will be measured from whole blood samples obtained and analyzed in a blinded fashion by the clinical laboratories at Hennepin Healthcare and MPHIC; both laboratories use methods certified by the National Glycohemoglobin Standardization Program. Both laboratories are certified by the College of American Pathologists.

- Baseline hemoglobin A1c values will be drawn at the baseline study visit, abstracted from the electronic medical records, or reported from an self-check A1c test kit. A1c values drawn up to two weeks prior to the baseline visit date as part of usual clinical care may be used as the baseline A1c value.
- Hemoglobin A1c values at 3 months (primary outcome) will be drawn at the 3 month study visit, or abstracted from the electronic medical records, or reported from an self-check A1c test kit. A1c values drawn up to two weeks prior or 4 weeks after the 3 month visit date as part of usual clinical care may be used as the baseline A1c value.
- Hemoglobin A1c values at 6 months will be abstracted from the electronic medical records at both institutions. A1c levels drawn 5-7 months after the baseline value will be recorded.

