- Cholesterol values at 3 months will be drawn at the 3 month study visit. Recent values recorded as part of usual clinical care within two weeks prior to the visit may be abstracted from the electronic medical records.
- Subsequent cholesterol levels will not be drawn or abstracted.

The total volume of whole blood drawn from each participant will be approximately 8 mL (3 mL for hemoglobin A1C testing and 5 mL for cholesterol testing) when visiting the lab. Over-the-counter A1c Test kits will be mailed to patients unable to visit the lab. Study staff will call patients to confirm reception of kit and go through the instructions.

All study tasks can be completed in-person in the clinical setting, virtually, or a combination of both, to accommodate the growing interest of patients to perform tasks virtually, when possible. This flexibility is noted in the Study Tasks Table below.

The number of diabetes-related office visits will be abstracted from the electronic medical records and categorized as a visit with a primary care provider, endocrinologist, pharmacist, care manager, diabetes educator, dietician, community health worker or promotora. These visits will be recorded for the six-month interval before and after intervention (or control) delivery.

Theory-based measures. We will measure diabetes-related self-efficacy with the Diabetes Self-Efficacy Scale ($\alpha=0.85$)¹¹⁷, used in other studies with Spanish-speaking patients¹¹⁸, including one from our study team that we used to generate preliminary data for this proposal²². We will measure diabetes-related outcome expectations with the Outcome Expectancies Questionnaire¹¹⁹, and social support for diabetes with items from the Diabetes Care Profile¹²⁰, which we also used in our pilot study.

Story identification and transportation will be assessed through a 14-item scale developed by Larkey and colleagues that demonstrated very good construct validity among Hispanic, Spanish-speaking populations^{121,122}, with initial predictive validity on the transportation (emotional engagement) scale⁸⁴.

Intervention follow-up exposure. During follow-up measures, we will assess the number of times each participant viewed the digital storytelling videos and whether they viewed it with friends or family. This will provide an assessment of intervention dose for the intervention group following the supervised viewing at enrollment.

Table 2. Measures

Data Collected	Baseline	6 weeks	3 months	6 months

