racial/ethnic minority populations, which showed a similar hemoglobin A1c reduction of 0.31 standard deviations¹²⁸. While these effects sizes are smaller than that of our pilot study, we have picked the more conservative (lower) estimate of effect size to ensure ample sample size. Hence, we can expect an effect likely to be between 0.25 and 0.31 standard deviation for the type of intervention proposed. Required sample sizes for an independent samples t-test to detect these two effect sizes, assuming 80% power, a two-tailed alternative and a 5% Type I error rate, are 252 and 145 patients per group, respectively. With 200 patients per group, we will have 80% power to detect an effect size of 0.28 standard deviations via the independent samples t-test. Accounting for approximately 12% loss to follow-up, we intend to recruit 225 patients in each group, for a total sample size of 450 participants.

Data analysis plan

Aim #1: Evaluate the efficacy of a community-derived digital storytelling intervention among Hispanic adults with poorly controlled T2D.

The primary analysis will be an independent samples t-test between the group average hemoglobin A1c values at 3 months. A two-sided alternative with a 5% type I error rate will be employed.

Supplementary analysis for the primary endpoint. Repeated measures modeling of the individual time point A1c values (including chart abstracted values at approximately 6 months) will allow for a more detailed investigation to the timing of the impact of the intervention by including all time points (including baseline). Profile analysis (Srivastava) will further assess for difference in overall means, time point, and treatment by time interactions. Covariates indicated above including demographics and clinical covariates will be included in the repeated measures and profile analysis models to assess the sensitivity of the primary analysis conditional on these potential concomitant (mediating) influences.

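### The primary t-test on 3-month A1c is valid but leaves out baseline A1c; a prespecified ANCOVA on a pre-randomisation baseline would raise power without extra patients or visits

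*Combined protocol and SAP*

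**What the plan says.** - **Primary test** (Data analysis plan, Aim #1): "The primary analysis will be an independent samples t-test between the group average hemoglobin A1c values at 3 months", two-sided at 5%.
- **Use of baseline** (Supplementary analysis for the primary endpoint): repeated-measures modelling of A1c "will allow for a more detailed investigation to the timing of the impact of the intervention by including all time points (including baseline"). Profile analysis and covariate-adjusted versions follow, as checks on the sensitivity of the primary result.
- **Sample size** (Sample size considerations): "With 200 patients per group, we will have 80% power to detect an effect size of 0.28 standard deviations via the independent samples t-test". The expected effect is 0.25 to 0.31 SD, and 0.25 SD is said to need 252 per group.
- **Baseline A1c** (Primary outcome measure): "Baseline hemoglobin A1c values will be drawn at the baseline study visit, abstracted from the electronic medical records", or reported from a self-check kit. Usual-care values from the fortnight before the baseline visit are accepted. Table 2 schedules A1c at baseline for everyone.
- **3-month A1c** (same section): the bullet ends by saying that usual-care values up to "4 weeks after the 3 month visit date as part of usual clinical care may be used as the baseline A1c value".
- **Kits** (Secondary outcome measures): "Over-the-counter A1c Test kits will be mailed to patients unable to visit the lab".
- **Order of events** (Recruitment, Enrollment, Randomization, and Retention): "Study staff will then obtain a baseline survey and biometric assessment (see measures) followed by randomization procedures (stratified by gender").
- **Secondary endpoints** (Secondary analyses): the same t-tests and repeated-measures models. The Measures section lets surveys be done "at clinic visits or by phone within 2 weeks following the clinic appointment".

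**The concern.** The test that decides the trial compares raw 3-month means. A1c before randomisation usually predicts A1c three months later, so part of the spread in the outcome is predictable from data already scheduled. The t-test treats that part as noise. The supplementary models will give baseline-informed estimates, but they do not pass the precision on to the result labelled primary.

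This matters because the plan says it works from the lower effect estimate, 0.25 SD, which by its own figures needs 252 per group, and then settles on 200.

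Bringing baseline into the primary model makes its definition important. A baseline value taken after randomisation can carry some of the treatment effect, and adjusting for it pulls the estimate towards zero. The current wording does not fully exclude this.

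**Working it through.** **Inputs from the plan.** 200 analysed per group; two-sided 5%; effects of 0.28 and 0.25 SD; pilot SDs from Table 1 (baseline A1c 2.5 and 2.1; change 2.0 and 1.8; 13 per group).

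**Assumptions.** The correlation rho between baseline and 3-month A1c is not stated, so a range is shown. Effects are taken in SDs of 3-month A1c.

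**1. The plan's own figures.** Noncentral t with 398 df gives 79.8% power at 0.28 SD, which reproduces the stated 80%. For 0.25 SD and 80% power the requirement is 252 per group, also as stated. With 200 per group, power at 0.25 SD is 70.3%. (The stated 145 per group at 0.31 SD does not reproduce; I get 164. Nothing below depends on it.)

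**2. ANCOVA.** Adjustment multiplies the residual variance by (1 − rho²), so the standardised effect becomes d/√(1 − rho²). The model has arm, baseline and gender, so df = 396. No gain is credited to gender.

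| rho | Power at 0.28 SD | Power at 0.25 SD | CI width relative to t-test |
|---|---|---|---|
| t-test | 79.8% | 70.3% | 1 |
| 0 | 79.8% | 70.3% | 1 |
| 0.22 | 81.7% | 72.5% | 0.98 |
| 0.3 | 83.4% | 74.4% | 0.95 |
| 0.5 | 89.7% | 82.1% | 0.87 |
| 0.65 | 95.7% | 90.7% | 0.76 |

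With 200 per group, 80% power at 0.25 SD is reached at rho of about 0.46. The number per group for 80% power at 0.25 SD falls from 252 to 230, 190 or 147 at rho 0.3, 0.5 or 0.65.

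**3. What the pilot suggests about rho.** rho = (sb² + sf² − sc²)/(2·sb·sf), where b, f and c denote baseline, follow-up and change.
- Pooled sb = √((2.5² + 2.1²)/2) = 2.31 and sc = √((2.0² + 1.8²)/2) = 1.90. The follow-up SD, sf, is not reported.
- The smallest rho for any sf is √(1 − 3.62/5.33) = 0.57, at sf = 1.31. It is 0.66 at sf = 2.31 and 0.69 at sf = 2.5.
- Fisher z limits with SE 1/√22 run from 0.22 (around 0.57) to 0.85 (around 0.69).
- The pilot was not randomised, took patients with A1c above 7% and used follow-up to six months. Entry at 8% or more, together with mixed A1c sources, could lower rho.

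**4. Missing baselines (illustrative: 10% missing, 0.25 SD, rho 0.3).**
- Complete-case ANCOVA keeps 180 per group: 69.8%, so the gain is lost. Break-even with the t-test is at rho = √0.10 = 0.32.
- Pooled mean plus missing indicator: residual variance 0.10 + 0.90 × 0.91 = 0.919, giving 73.9%.

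**5. Misdated baselines (illustrative).** If a fraction p of baselines were really 3-month values, the estimate would be multiplied by about 1 − p·((1 − p)·rho + p). At rho 0.5 this is 0.945 for p = 0.10 and 0.880 for p = 0.20. Simulation with 6,000 runs gave 0.942 and 0.883.

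**The case against.** The strongest reply is that nothing here is wrong. The t-test is valid under randomisation, matches the sample size method, and is accompanied by models that do use baseline. The 70% power at 0.25 SD comes from choosing 200 per group, which the plan discloses. All of this is true, and it is why the point is an improvement rather than a correction. But the supplementary models do not decide the trial.

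Other points narrow the case without removing it:

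- **Order of events.** The recruitment section puts the baseline survey and biometric assessment before randomisation, and the usual-care window for baseline A1c runs only backwards. The remaining gap is that this ordering does not name A1c or kits, while remote participation and mailed kits are allowed.
- **Misdating figures.** The 3-month bullet is probably a drafting slip and the fractions are invented. A kit result arriving shortly after randomisation would carry less treatment effect than a 3-month value. The 6% and 12% shrinkage only illustrates the mechanism.
- **Missing baselines.** Eligibility requires a most recent A1c of at least 8%, so an earlier value, possibly older than two weeks, exists for every eligible patient. The 10% missing is an assumption. Without a missing-data rule, complete-case ANCOVA can fall slightly below the t-test (67.9% against 70.3% at 0.25 SD and rho 0.22).
- **Pilot correlation.** The 0.57 floor uses pooled, rounded SDs. The control arm alone gives √(1 − 3.24/4.41) = 0.515, or about 0.43 at the rounding limits.
- **Effect units.** The pilot's 0.37 is 0.7/1.90, a change-score SD. If 0.28 were in those units (equal SDs, normal approximation), t-test and ANCOVA power would be 91% and 93% at rho 0.3, 80% and 90% at 0.5, and 58% and 86% at 0.7. The levels move, but ANCOVA stays ahead.
- **Timing.** The COVID-19 adaptations suggest, without proving, that the study is under way. Changing a primary analysis then needs clear documentation.

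**Conclusion.** The concern holds as a recommended improvement. The planned test is sound but does not use baseline A1c. Over rho 0.22 to 0.65, adjustment adds about 2 to 16 percentage points of power at 0.28 SD and 2 to 20 at 0.25 SD, and at rho 0 it costs less than 0.1 point. The direction is firm provided that baseline is measured before randomisation and participants with a missing baseline are kept in the model. The size rests on a correlation that the plan does not give and that a pilot of 13 per group cannot fix.

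**What to change.** By a documented amendment before unblinding:

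1. Make the primary analysis an ANCOVA of 3-month A1c on arm, baseline A1c and gender, two-sided 5%. Keep the unadjusted t-test as a sensitivity analysis.
2. Define baseline A1c as a value obtained before randomisation, whether from laboratory, chart or kit. Treat any later value as a missing baseline.
3. Reconcile the 3-month bullet under Primary outcome measure, which refers to the baseline value.
4. Prespecify the handling of missing baselines, for example the baseline mean pooled over both arms plus a missing indicator, so that no randomised participant with a 3-month value is dropped.
5. Use the same baseline-adjusted model for the SDSCA subscales, blood pressure, LDL-cholesterol and BMI, with the same pre-randomisation rule. For surveys, reconcile the two-week phone allowance with the section that places the baseline survey before randomisation.

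The cost is one amendment and a clarified definition. There are no added patients, visits or blood draws. The documents do not settle whether enrolment has begun; if it has, the amendment should state that no unblinded data were seen.

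### The primary t-test on observed 3-month A1c leaves baseline A1c unused and the expected 12% loss without a stated method

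*Combined protocol and SAP*

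**What the plan says.** The combined protocol and SAP, Data analysis plan, Aim #1, defines the primary analysis in two sentences: "The primary analysis will be an independent samples t-test between the group average hemoglobin A1c values at 3 months" and "A two-sided alternative with a 5% type I error rate will be employed". Baseline A1c does not enter the test, although the Measures section collects it for every participant.

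Sample size considerations ties the design to the same test: "With 200 patients per group, we will have 80% power to detect an effect size of 0.28 standard deviations via the independent samples t-test". It then inflates for loss: "Accounting for approximately 12% loss to follow-up, we intend to recruit 225 patients in each group, for a total sample size of 450 participants".

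The supplementary analysis does use baseline: "Repeated measures modeling of the individual time point A1c values", with 6-month chart values and covariates. Its stated purposes are the timing of the effect and sensitivity to covariates. Missing outcomes are not mentioned there.

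The document states no analysis population, imputation, missing-data assumption or missing-data sensitivity analysis. Missing data appear only as an item in the statistician's monthly data checks (Study Coordinator Training and Quality Assurance). The plan does not use the term complete-case, but a t-test with no imputation can use only participants who have a 3-month value.

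**The concern.** Two things are at stake.

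The first is precision. Baseline A1c usually predicts later A1c, and a test that ignores it carries variance that could be removed at no recruitment cost. This matters here because the plan sizes the trial for 0.28 SD, while the lower effect it cites, 0.25 SD, needs 252 per group by its own figures.

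The second is loss to follow-up. The comparator is usual care with no sham video, so participants know their arm. The monthly texts recommend the video, so they read as intervention-arm only. A 3-month A1c may also be taken from the usual-care record, so clinic attendance helps to decide whether the outcome is seen. If loss depends on A1c differently in the two arms, the observed-case difference shifts, and nothing in the primary analysis corrects for this or shows how much it matters.

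**Working it through.** **Inputs from the document.** Two-sided alpha 0.05; 200 evaluable and 225 recruited per group; about 12% loss; target 0.28 SD; lower cited effect 0.25 SD. Pilot Table 1, 13 per group: baseline SD 2.5 (intervention) and 2.1 (control); SD of change 2.0 and 1.8.

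**Assumptions.** The document gives neither the correlation r between baseline and 3-month A1c nor loss by arm. Both are varied below.

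**1. The plan's own figures.**
- Required n per group = 2 × (1.96 + 0.8416)² / d² = 15.70 / d². For d = 0.25 this is 15.70 / 0.0625 = 251.2, so 252, as stated.
- With n = 200 and d = 0.28: √(2/200) = 0.100, 0.28 / 0.100 = 2.80, and Φ(2.80 − 1.96) = 80%, as stated.
- With 12% loss, 225 × 0.88 = 198 remain, and power is 79.6%.
- The stated 145 for 0.31 SD does not reproduce (15.70 / 0.0961 = 163.4, so 164). This does not affect the present point.

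**2. What baseline says about r.** If the follow-up SD equals the baseline SD, then SD(change)² = 2 × SD² × (1 − r).
- Intervention: r = 1 − 4.00 / (2 × 6.25) = 0.68.
- Control: r = 1 − 3.24 / (2 × 4.41) = 0.63.

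These come from 13 patients per group with A1c above 7%. The trial requires 8% or more, and a narrower baseline range tends to lower r, so 0.3 to 0.7 is shown.

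**3. Power with baseline adjustment.** Adjustment multiplies the residual variance by 1 − r². Power = Φ(d / [√(1 − r²) × √(2/n)] − 1.96), with n = 198. Example: d = 0.28, r = 0.5 gives 2.786 / 0.866 = 3.217, and Φ(1.257) = 90%.

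| Effect | Unadjusted | r = 0.3 | r = 0.5 | r = 0.66 | r = 0.7 |
|---|---|---|---|---|---|
| 0.28 SD | 80% | 83% | 90% | 96% | 97% |
| 0.25 SD | 70% | 74% | 82% | 91% | 94% |

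Using n = 200 changes these by less than half a percentage point. At r = 0.5, the number needed for 0.25 SD falls from 252 to 0.75 × 252 = 189 per group, which the trial would have.

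**4. Bias from loss.** Simulation with 1,000,000 per arm, true effect zero and logistic dropout. Loss is 12% in each arm except in the 6% v 18% row. Negative values favour the intervention; swapping the arms reverses the sign.

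| Assumed loss | t-test bias in SD, r = 0.3 / 0.5 / 0.7 | Baseline-adjusted bias |
|---|---|---|
| Same rate and mechanism in both arms | about 0 | about 0 |
| Rises with baseline A1c in the intervention arm only (odds ratio about 2 per SD) | −0.02 / −0.04 / −0.06 | about 0 |
| Opposite baseline slopes in the two arms | −0.05 / −0.08 / −0.11 | about 0 |
| Same baseline slope, loss 6% v 18% | −0.02 / −0.04 / −0.06 | about 0 |
| Rises with the unseen 3-month A1c, intervention arm only | about −0.08 throughout | −0.07 / −0.06 / −0.04 |

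In the baseline-driven rows the bias is r times the between-arm difference in completers' baseline mean. In the second row that difference is about 0.08 SD, and r × 0.08 gives 0.024, 0.040 and 0.056. In the third row it is about 0.16 SD, giving 0.048, 0.080 and 0.112. The t-test's type I error is 5.7% / 7.0% / 8.6% in the second row and 7.8% / 12.4% / 20.0% in the third, against a nominal 5%.

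**The case against.** A reader might infer that this is an unblinded trial whose t-test will favour the intervention. The document does not support that. Under Measures, investigators and analysts are to stay blinded and laboratory A1c is analysed blinded; participants and the staff who deliver the video are the ones who know the arm. Coordinator attention is to be balanced. Loss by arm is not given.

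The direction is open too. More text contact and more clinic contact in the intervention arm would tend to improve A1c capture there. Loss would then be higher in control, and if those lost have high A1c, the t-test would be biased against the intervention.

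A missed visit also need not mean a missing outcome. The 3-month value may come from the visit, the record or a self-check kit, within 2 weeks before to 4 weeks after the due date, and kits are mailed to those unable to attend. Reminder calls, letters and remuneration apply to participants generally. These steps should reduce loss, but the plan still allows for about 12%.

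Finally, the repeated-measures model is already planned, and the stated 80% power at 0.28 SD is correct for the test chosen. Both are true. They make the change easy, but they do not supply a missing-data method for the primary result. The precision gain stands whether or not loss differs by arm.

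**Conclusion.** The point holds as one of lost precision and an unstated missing-data method. Power at 0.28 SD is 80% as planned, against 83% to 97% with baseline adjustment for r from 0.3 to 0.7. At 0.25 SD it is 70% against 74% to 94%. The size rests on r, for which the only evidence is a small pilot and an equal-SD assumption; any r above zero gives some gain.

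Bias is a possibility of about 0.02 to 0.11 SD in either direction (7% to 39% of 0.28 SD) under the baseline-driven patterns assumed here, and about zero if loss behaves alike in both arms. It would also be wrong to infer that a better model settles the missing-data question. It removes bias that depends on arm and baseline A1c, but only part of any bias that depends on the unseen 3-month value, so a sensitivity analysis is still needed.

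**What to change.** In the Data analysis plan, Aim #1:

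- Make the primary analysis a likelihood model of baseline and 3-month A1c with a common baseline mean across arms, in all randomised participants in their assigned arm. Report the 3-month difference with its 95% confidence interval.
- State the missing-data assumption this makes: loss may depend on arm and observed A1c.
- Keep the independent samples t-test as a sensitivity analysis.
- Add a delta analysis that shifts missing 3-month values in each arm separately and in both directions, for example by 0.5 and 1.0 A1c points, and report where the conclusion changes.
- Report loss by arm and by baseline A1c.

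The change should be made before any comparison by arm is seen, since two A1c analyses are already planned. The cost is SAP wording and slightly more analysis, with no new data. The downside is that the primary estimate comes from a model and not from a simple difference in means.

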Secondary analyses. The analyses applied to the primary endpoint will also be applied to each of the secondary endpoints. The subscales from the SDSCA (general diet, diabetes diet, physical activity, diabetes medication use, blood glucose monitoring) and the physical measurements (blood pressure, LDL-cholesterol, BMI) will be compared between groups using t-tests and repeated measures monitoring similar to the primary endpoint. As we have a *single variable* primary endpoint defined, there will be no adjustment for comparison-wise Type I error rate. Additional analyses will be performed to identify potential effect modifiers for the primary and secondary outcomes, i.e., sex, age, socioeconomic position, acculturation, health literacy, and diabetes knowledge.

Aim #2: Explore the effect of the digital storytelling intervention on proposed theory-based mediators of change.

We will examine the correlational structure of the covariates and their impact on the intervention effect size via repeated measures models. We will include procedures suggested by MacKinnon^{129,130} to assess mediation, fitting three general estimating equation models to the data. We will first estimate the intervention effect separately for the dependent variable (with regression adjustment for covariates); that model provides an estimate of the total effect of the intervention. Next, we will estimate the intervention effect for each mediator (with regression adjustment for covariates); that model provides an estimate of the effect of the intervention on the mediator. Finally, we will estimate the mediated intervention effect for the dependent variable by adjusting for the mediator (and covariates); that model provides an estimate of the unmediated (i.e., direct) intervention effect, and the intervention-adjusted effect of the mediator on the dependent variable. These analyses will be done for the primary endpoint and each of the secondary endpoints to identify any mediators of the study results.

Table 3. Study Timeline

Tasks to be completed	Year 1	Year 2	Year 3	Year 4
Recruitment, enrollment, and baseline measures				
Intervention				
Follow-up measurements				
Data analysis				
Dissemination and sustainability plan				

Dissemination and Sustainability Plan

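### The overall-means test in the supplementary profile analysis averages in the pre-randomisation baseline, which dilutes any treatment effect, and the plan does not say which profile test carries that effect

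*Combined protocol and SAP*

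**What the plan says.** In the combined protocol and SAP, under Data analysis plan, Aim #1, the primary analysis is clear: "The primary analysis will be an independent samples t-test between the group average hemoglobin A1c values at 3 months". The paragraph on supplementary analysis for the primary endpoint then adds repeated-measures modelling, meant to examine the "timing of the impact of the intervention by including all time points (including baseline"). The next sentence is: "Profile analysis (Srivastava) will further assess for difference in overall means, time point, and treatment by time interactions". Demographic and clinical covariates enter these models so that the sensitivity of the primary result can be judged. Baseline HbA1c appears there as one of the outcome times and is not named as a covariate.

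The section on recruitment, enrollment, randomization and retention places the baseline assessment before randomisation. Table 2 schedules HbA1c at baseline, 3 months and 6 months. Blood pressure, LDL-cholesterol and BMI are scheduled at baseline and 3 months only.

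Under Secondary analyses: "The analyses applied to the primary endpoint will also be applied to each of the secondary endpoints". The sentence after it, which lists the self-care subscales and physical measurements, names t-tests and repeated-measures work but not profile analysis.

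**The concern.** A treatment given after baseline cannot move the baseline mean. A test of overall means that counts baseline as one of its visits therefore compares a diluted effect plus whatever chance imbalance existed at baseline. Nothing in the plan leaves baseline out of that mean, sets the two baseline means equal, or says which of the profile tests represents the treatment effect.

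The supplementary models are there to show how robust the primary result is. If the overall-means line is non-significant beside a significant 3-month t-test, a reader could take this as a failed sensitivity check when the cause is the construction of the test.

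**Working it through.** **Inputs from the plan.** Two-sided 5% test ("A two-sided alternative with a 5% type I error rate will be employed"). Sample size section: "With 200 patients per group, we will have 80% power to detect an effect size of 0.28 standard deviations via the independent samples t-test". Pilot Table 1: baseline SD 2.5 and 2.1, SD of change 2.0 and 1.8, 13 patients per group.

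**Assumptions (not in the plan).** Equal SD at each visit, set to 1. Equal correlation r between visits. Effect d = 0.28 at 3 and 6 months unless stated otherwise. All 200 per group have every value.

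**Correlation implied by the pilot.** With equal SDs, r = 1 − (SD of change)² / (2 × SD²).
- Intervention: 1 − 4.00/12.50 = 0.68
- Control: 1 − 3.24/8.82 = 0.63
- From averaged variances: 1 − 3.62/10.66 = 0.66

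**Plan's own figure.** The standard error of a group difference is SD × √(2/200) = 0.1 × SD. So z = 0.28/0.1 = 2.80, and power = Φ(2.80 − 1.96) = 80%. This reproduces.

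**Overall means, HbA1c (three visits).** Effect = (0 + 0.28 + 0.28)/3 = 0.187. SD of a patient's mean = √((1 + 2r)/3).

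| r | SD | z | Power |
|---|---|---|---|
| 0.3 | 0.730 | 2.56 | 72% |
| 0.5 | 0.816 | 2.29 | 63% |
| 0.66 | 0.879 | 2.12 | about 56–57% |

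Break-even with the primary t-test is (2/3)/√((1 + 2r)/3) = 1, so (1 + 2r)/3 = 4/9 and r = 1/6. At r = 0 the overall-means test has 90% power.

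**If the effect is not constant.** The retained fraction is 1/2 if the effect halves by 6 months, 1/3 if it is gone, and 5/6 if it grows to 1.5 times. At r = 0.66, power is then 36%, 19% and 76%.

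**Treatment by time, HbA1c.** This is a Hotelling test on the two changes from baseline. The noncentrality is 100 × 0.28² × (2/3)/(1 − r) = 5.227/(1 − r), that is 7.47, 10.45 and 15.37 at r = 0.3, 0.5 and 0.66. Power on 2 and 397 df is 68%, 83% and 95%.

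**Overall means, two-visit endpoints.** Effect = 0.28/2 = 0.14. SD = √((1 + r)/2).

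| r | SD | z | Power |
|---|---|---|---|
| 0 | 0.707 | 1.98 | 51% |
| 0.3 | 0.806 | 1.74 | 41% |
| 0.5 | 0.866 | 1.62 | 37% |
| 0.66 | 0.911 | 1.54 | 34% |

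**Baseline as covariate, mean of 3 and 6 months, HbA1c.** Effect = 0.28. Variance = (1 + r)/2 − r² = 0.560, 0.500 and 0.394 at r = 0.3, 0.5 and 0.66. So z = 3.74, 3.96 and 4.46, and power is 96%, 98% and 99%.

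**The case against.** The strongest reply is that the sentence on profile analysis lists more than overall means. Its treatment-by-time test uses baseline as the reference and loses nothing to dilution. At r of 0.5 or more it has more power than the primary t-test. By convention the level test in a profile analysis is read only when the profiles are parallel, and a real post-baseline effect makes them non-parallel. The stated purpose of the repeated-measures work is also timing, which is a visit-specific question. All of this stands. A reader might infer that profile analysis as a whole is weaker than the t-test, but the calculation does not support that.

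Two further inferences go too far. A fixed loss of one third needs equal effects at 3 and 6 months, which the plan does not state. Lower power does not follow from dilution alone either, because averaging also reduces variance; for HbA1c with a sustained effect it needs r above 1/6.

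The value 0.66 is soft. It comes from 13 patients per group with an equal-SD assumption, and the pilot subset had HbA1c above 7% whereas the trial requires at least 8%. The carry-over to secondary endpoints is also open to reading, since only the general sentence implies it.

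One might add that profile analysis drops patients with no 6-month chart value. The documents describe no missing-data handling, so that would be an assumption, and this point does not rest on it.

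What the reply does not remove is the absence of a rule. The plan sets a diluted and an undiluted test side by side and does not say which one speaks to treatment.

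**Conclusion.** The point holds for one of the supplementary tests, not for profile analysis in general. With a sustained effect of 0.28 SD and 200 per group, the overall-means test for HbA1c has 72%, 63% and about 56–57% power at r = 0.3, 0.5 and 0.66, against 80% for the primary test. If the general sentence under Secondary analyses extends it to blood pressure, LDL-cholesterol and BMI, half the effect is lost, and power for the same effect size is 51% at r = 0 falling to 34% at r = 0.66. These figures rest on equal SDs, equal correlations and complete data.

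A reader might infer that the trial's main conclusion is at risk. It is not: the primary t-test, its alpha and the sample size do not depend on this analysis. The consequence is a sensitivity result that could be misread, which is worth correcting because the correction costs so little.

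**What to change.** State in the SAP that an overall-means comparison that includes baseline will not be used as evidence of a treatment effect. Fit the repeated-measures model already planned with the post-baseline visits as outcomes and baseline as a covariate, or with one baseline mean common to both arms. Report the treatment effect at 3 months, at 6 months where measured, and averaged over the post-baseline visits. Use the same form for the secondary endpoints. Where only 3 months follows baseline, this reduces to a baseline-adjusted 3-month comparison.

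For HbA1c the averaged post-baseline effect has 96–99% power at the correlations used here if all 200 per arm have both values, and less where 6-month chart values are missing. The cost is SAP wording only, and all the data are already scheduled for collection.
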